10.11. Study instrument(s) and outcome measurement(s)

The ventilator modes for nSIPPV and nHFO are SLE 6000 (United Kingdom). Nasal mask for interface. Blood gas and electrolytes analyzer ABL800 BASIC (Radiometer Medical ApSTM, Denmark).

10.12. Data collection methodology

Participant's data and blood gas's result will be recorded in record form.

10.13. Data management

EpiData entry is used for data entry and data documentation. The data will be safe and private collected; moreover, only principal investigator and recorder will access.

10.14. Statistical analysis

Descriptive part: Mean (SD), Median \pm IQR

Analytic part: Continuous outcome

1. Carry-over effect = Independent t-test comparing intraindividual sums of measurements from both periods.
2. Treatment effect = Independent t-test comparing intraindividual differences of measurements of nHFOV versus nSIPPV from both periods.
3. Dependent t-test

Regression analysis

Category (reintubation): logistic regression

Time to event (reintubation): Cox's proportion model

Intention-to-treat analysis was applied in case of treatment failure.

$p < .05$ was considered significant

Subgroup analysis was performed

11. Ethical consideration

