3		Unknown [†]	Nasal High Frequency Oscillatory Versus Nasal Intermittent Positive Pressure Ventilation in Neonate After Extubation	
 • Respiratory Insufficiency 	
 • Device: NIPPV • Device: NHFOV 	

[†] Study has passed its completion date and status has not been verified in more than two years.

Activate Windows [^ TO TOP](#)
Go to Settings to activate Windows.

[figure not shown]
[For Patients and Families](#) | [For Researchers](#) | [For Study Record Managers](#)

7. Objective(s) of the study

Primary objective: To assess the pCO₂ after 2 hours of nHFO compared with 2 hours of nSIPPV in crossover study.

Secondary objective: To assess the reintubation rate within 7 days between non-invasive ventilations (nHFO vs nSIPPV) from the latter NIV mode in parallel study

8. Study flow diagram and/or Conceptual framework

9. Literature review

Mechanical ventilation was introduced to treat respiratory failure in preterm infants or sick neonates then improvements in survival.^{1,2} However, the complications from short or long term use of ventilation can result in unintended harm or burden (e.g., air leak syndrome, pneumonia, bronchopulmonary dysplasia, neurological injury, retinopathy of prematurity).^{3,4} To reduce these risks, clinicians should aggressive extubated neonates as early as possible. Respiratory (focus on blood gas as well as partial pressure CO₂ [pCO₂]) or extubation (focus on clinical condition as well as reintubation) failure was worrisome in pediatrician and parents if the neonate was reintubated owing to complete recovery of lung disease or inadequate respiratory drive.

[figure not shown]
[figure not shown]
[figure not shown]
Non-invasive ventilation (NIV) was supported for primary respiratory support (initial mode before endotracheal intubation) or post-extubation. Nasal continuous positive airway pressure (nCPAP) was familiar to NIV mode in neonatal respiratory support. Nowadays, the new NIV modalities are nasal intermittent synchronized positive pressure ventilation (nSIPPV) and nasal high frequency oscillation (nHFO).

[figure not shown]
[figure not shown]
[figure not shown]

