10.10. Study procedure(s)/stage(s)

[figure not shown]
This study was blocked and stratified randomization. Subjects were equally (1:1) randomized to one of the two treatment sequences (nHFOV–nSIPPV, nSIPPV–nHFOV). The allocation sequence was computer generated by box of four. The allocation concealment was ensured by using identical, opaque, sealed envelopes. An envelope was drawn by a dedicated nurse immediately after enrolment of the infant. The participants were stratified by gestational age and oxygen index (OI = mean airway pressure [MAP]*FiO₂*100/PaO₂). The participants were on the non-blinded and randomized NIV mode for 2 hours and blood gas was analyzed then switched to another NIV mode for 2 hours (cross-over) and blood gas was analyzed repeatedly. There was not a washout period between 2 NIV modes then the last NIV mode was on until no need NIV. We will register in ClinicalTrials.gov before start and enrollment of the participants.

Extubation criteria: The ventilated neonate had a targeted oxygen saturation (SpO₂ > 90%) during on FiO₂ < 0.4 and acceptable blood gas (pH > 7.25, PaCO₂ < 60) with the respiratory setting of

[figure not shown]
1. HFO: flow 6-10 L/min, frequency 10 Hz, MAP = “6-7 (preterm), 7-9 (term)” cmH₂O, dP = 12-20, I:E = 1:1
2. AC: flow 6-10 L/min, rate 30/minute, PIP 12-15 cmH₂O, PEEP = 3 cmH₂O

Intervention nHFOV and nSIPPV were generated by neonatal ventilators (SLE6000 infant ventilators, United Kingdom) using bi-nasal prongs (RAM cannula, NEOTECH[®], USA) or the nasal mask of the same type for both ventilation modes. The size of the prongs was determined by the infant's weight. The largest possible prongs were used, with a snug fit to avoid leakage. Pacifier for preterm and term neonate (JollypopTM, USA) was taken to avoid leakage from the mouth. The disposable ventilator circuit (Fisher & Paykel RT268TM, Evaqua Dual Limb Infant Breathing Circuit Kit with Evaqua 2 Technology and Pressure Line, Flow > 4L/min, New Zealand) was used. The initial NIV setting was⁷

1. nHFO: flow 8-10 L/minute, frequency 10 Hz, MAP = "MAP (before extubation) + 2" or "8 (preterm), 10 (term)" cmH₂O, dP = "2-3 times of MAP with visible chest oscillations" or 25-35 cmH₂O, I:E = 1:1, FiO₂ = "FiO₂ (before extubation) + 0.1-0.2" keep targeted SpO₂ 90-94%

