2. nSIPPV: flow 8-10 L/minute, rate 60/minute, PIP = "PIP (before extubation) + 2-5" or "20 (preterm), 25 (term)" cmH₂O, PEEP = 5 cmH₂O, IT = 0.5 s, FiO₂ = "FiO₂ (before extubation) + 0.1-0.2" keep targeted SpO₂ 90-94%. The highest trigger sensitivity avoiding auto triggering was selected.

The monitoring after extubation was vital signs, clinical manifestations, respiratory distress, and umbilical arterial blood gas. The first blood gas before extubation was routine obtained. After randomization, the initial NIV was started then blood gas was obtained after 2 hours. The participant was switched to another NIV and blood gas was obtained after 2 hours. The participant was continued with the last NIV mode until the NIV was stopped. The participant was excluded if severe respiratory failure with reintubation during 4 hours after intervention. The parameters were adjusted or titrated according to patient tolerance and disappeared respiratory distress, the intervention went on until 4 hours. The NIV was stopped to "room air, oxygen box, low or high flow cannula" when

1. nHFO: MAP = 5-6 cmH₂O, dP = 10-15
2. nSIPPV: PIP/PEEP = 10-12/3-5 cmH₂O

Criteria for extubation failure or reintubation were as follows:

1. Cardiorespiratory arrest or any type of pulmonary hemorrhage
2. Persistent low blood pressure without response to volume expander and vasoactive agents
3. Stupor or persistent drowsiness after initial correction and care
4. Severe respiratory distress
5. Two hours of respiratory acidosis with PaCO₂ > 70 mmHg and pH < 7.2
6. Two hours of hypoxia with PO₂ < 50 mmHg with FiO₂ > 0.6, and maximal pressures given (MAP 20 and PIP 25 cmH₂O in the nHFOV and nSIPPV group, respectively)
7. Apnea occurring three or more times per hour and a heart rate less than 100/min or apnea with required bag-and-mask ventilation.
8. Severe post extubation stridor

In case of extubation failure, the study period was ended prematurely for the respective infant, pCO₂ was measured by blood gas analysis and a mode of ventilation was chosen as

deemed appropriate by the attending staff. In general, infants were treated with intravenous aminophylline then oral caffeine base and were supported before and after the study.

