11.5. Procedure specifying for research participant withdrawal from the study

If enrolled participant met the withdrawal criteria, the participant was withdrawal and not replaced. The subjects withdrawn were followed-up as routine care.

11.6. Clearly indicate person(s) responsible for payment for treatment of complications and adverse effects

None

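### Does the primary pCO₂ test, with its subtraction and groups left unstated, risk testing period instead of treatment?

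*Combined protocol and SAP*

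**What the plan says.** Section 7 sets the primary objective: "To assess the pCO₂ after 2 hours of nHFO compared with 2 hours of nSIPPV in crossover study". Section 10.10 randomises infants 1:1 to two sequences (nHFOV then nSIPPV, or the reverse), stratified and in blocks of four, with no washout.

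For the continuous outcome, Section 10.14 lists three items:

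- Item 1 looks for carry-over by means of sums: "Carry-over effect = Independent t-test comparing intraindividual sums of measurements from both periods".
- Item 2 turns to the comparison of the two modes by means of differences: "Treatment effect = Independent t-test comparing intraindividual differences of measurements of nHFOV versus nSIPPV from both periods".
- Item 3 only names a paired test: "Dependent t-test", with nothing further.

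Significance is p < .05. The section does not state the direction of subtraction in item 2, the two groups it compares, or the outcome and role of item 3. No other section supplies these.

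**The concern.** An independent t-test needs two independent groups, and the only randomised groups here are the sequences. If the quantity compared between them were nHFO minus nSIPPV, the treatment effect would drop out and the test would respond only to a change over time. Such a change is plausible. Period 1 is the first two hours after extubation, period 2 the next two, and "The parameters were adjusted or titrated according to patient tolerance and disappeared respiratory distress". A real effect could then be missed, or a time trend reported as a treatment effect.

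Item 3 adds a second worry. If it tests the same contrast, it has no period term. It loses power under a period shift, and it is biased when the sequences end up unequal. That can happen, because an infant who meets a withdrawal criterion is withdrawn and not replaced (Section 11.5). With two tests of one outcome and no stated order, the choice could be made after seeing the data.

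**Working it through.** **Plan's own figure.** Section 10.9 gives means 35.1 and 43 (difference 7.9) and SDs 7.5 and 6. With two-sided alpha 0.05 and 80% power, n = (1.96 + 0.842)² × (7.5² + 6²) / 7.9² = 11.60, so 12 per group as stated. The point at issue does not alter this.

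**Algebra.** Let τ be the nHFO minus nSIPPV effect and π the period 2 minus period 1 shift, with no carry-over.

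| Sequence | Period 1 − period 2 | nHFO − nSIPPV |
|---|---|---|
| nHFOV then nSIPPV | τ − π | τ − π |
| nSIPPV then nHFOV | −τ − π | τ + π |
| Difference between sequences | 2τ | −2π |

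Reading A (first column) tests treatment, whatever the period shift. Reading B (second column) tests period only.

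**Size.** Assumptions not in the documents: 24 infants (12 per sequence), within-infant correlation 0.5 (range 0.3 to 0.7), and period shifts of 3 or 5 mmHg. The SD of the within-infant difference is √(7.5² + 6² − 2 × 0.5 × 45) = 6.87. The standard error of the difference between sequence means is 6.87 × √(1/12 + 1/12) = 2.81.

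- Reading A at 7.9 mmHg: 2 × 7.9 / 2.81 = 5.6 standard errors, power 99.97%. With no effect it rejects 5%.
- Reading B at 7.9 mmHg with no period shift: 5%.
- Reading B with no treatment effect: 2 × 3 / 2.81 = 2.1 standard errors, 53% rejection (41–74%) for a 3 mmHg shift. For 5 mmHg, 2 × 5 / 2.81 = 3.6, 93% (83–99%).

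The two readings therefore differ greatly, and the question is which one Section 10.14 supports.

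**Which reading.** Three features point to A:

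- Item 2 is headed as the treatment effect. Reading B is a period test and contradicts that heading.
- It is an independent t-test, so it compares two groups, and the only two are the sequences.
- It directly follows the test of within-infant sums for carry-over. Sums for carry-over and period differences for treatment, each compared between sequences, form the textbook pair for a two-period crossover.

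The plan never says nHFOV minus nSIPPV. The phrase naming the two modes can simply identify the measurements being differenced.

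**Item 3, if it tests the same contrast.** Its mean is τ + π(n2 − n1)/(n1 + n2).

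- 12/12: unbiased. With a 5 mmHg shift, type I error is 1.6%, and power at 7.9 mmHg is 99.8% against nearly 100% for reading A.
- 13/11 with a 5 mmHg shift: bias 2/24 × 5 = 0.42 mmHg.
- 15/9 with a 5 mmHg shift: bias 6/24 × 5 = 1.25 mmHg.

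Simulating 24 infants in blocks of four, with 2 to 6 strata and 0–20% loss without replacement (assumed), the sequences differ by 2 or more infants in 37–65% of trials and by 6 or more in 0–4%.

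**Reporting the better of items 2 and 3.** By simulation at correlation 0.5 with shifts of 0 to 5 mmHg, type I error is about 5.0–5.5% at 12/12 or 13/11, and 6–9% at 15/9. Power at 7.9 mmHg at 12/12 or 13/11 is above 99% whichever test is used.

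**The case for a change.** The strongest reply is that a plan should fix its primary test without leaving the analyst to infer it, most of all in an unblinded trial. The only contrast item 2 names is between the two modes, and a literal reader could subtract that way. Even under reading A, items 2 and 3 carry no stated order and are both read at p < .05. At 15/9 with a 5 mmHg shift, a true effect of 4.61 mmHg would be estimated by the paired test as 5.86 or 3.36, with power 94% or 45% against 86% for the period-adjusted test.

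Part of this stands: the wording is incomplete, and a sentence giving the subtraction and the role of item 3 would be tidier. The predicted harm does not follow. Only item 2 carries the treatment-effect label, so the tests are not wholly unranked. The documents do not say what item 3 tests. Sections 10.10 and 11.1 describe blood gases before as well as after the intervention, so a paired before-and-after comparison is equally possible. The 4.61 mmHg example needs three things together: a rare split, a shift with no source in the documents, and an effect taken from a different comparison (nHFO against nBi-CPAP or nCPAP, Table 2).

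The bias also depends on a total of 24. Section 10.9 calculates 373 per group (401 with continuity correction) for reintubation and does not say which calculation sets enrolment. With 802 infants, 4 strata, 0–20% loss and a 5 mmHg shift, the mean absolute bias of the paired test is 0.01–0.07 mmHg. A larger total would not rescue reading B, but reading B is not the one the section supports.

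**Conclusion.** The concern does not call for a change. Section 10.14 omits the subtraction, the groups and the purpose of the paired test, but its heading, its choice of test and the companion test of sums identify the standard crossover analysis, which is valid under any period shift. An analyst would apply it that way. If the paired test is a second look at the same contrast, choosing the better result moves type I error from 5% to at most about 5.5% at 12/12 or 13/11, and to 6–9% only at a 15/9 split. Power at the planned 7.9 mmHg is hardly affected at 12/12 or 13/11.

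These sizes assume 24 infants, correlation 0.5, period shifts up to 5 mmHg and no carry-over. The conclusion that item 2 is the valid test rests on the text of the section and not on those values.

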11.1. Possible risks/effects in the study, including preventive and alleviation measures

Both interventions, the participants were obtained the blood samples before and after intervention via arterial line to minimize pain from phlebotomy.

The volume of blood sample was 0.4 mL including before and after tests. The maximum allowable blood draw volumes were shown in **Figure 6**.

Maximum allowable blood draw volumes:

PATIENT'S WEIGHT		TOTAL VOLUME	MAXIMUM mL IN ONE BLOOD DRAW	MAXIMUM mL IN A 30-DAY PERIOD
Kg	lbs	mL		
1	2.2	100	2.5	5
2	4.4	200	5	10
3	3.3	240	6	12
4	8.8	320	8	16
5	11	400	10	20

Figure 6 Maximum allowable blood draw volumes

11.2. Describe the process/system for assuring confidentiality and the privacy of the research participants/communities

The record form was unidentifiable enrolled patients; therefore, name or hospital number would not be filled in the record form. The data would be kept in secret files and only principal investigators and recorders could access to these data during recruitment of the participants, during data collection, during transcription, and data analysis, and dissemination of research results.

11.3. Benefits of the study for participants and the community/country including how findings of the study use for strengthening community.

The result of this study may be the choice of post-extubation via nSIPPV and nHFO (head to head comparison)

11.4. Informed consent process: Process/method of invitation the participants to participate in the research, such as personal contact, referral from other(s), brochure, and announcement, etc.

The parents of intubated neonates without exclusion criteria would be pursued to enrolled in this study by the dedicated nurse. The parents would receive informative documents with explaining the entire data about 30 to 60 minutes or until the parent were crystal clear about the study detail by the nurse. If the parents allowed the patients to enroll in the study, they would sign the signature in the informed consent's document.

11.5. Procedure specifying for research participant withdrawal from the study

If enrolled participant met the withdrawal criteria, the participant was withdrawal and not replaced. The subjects withdrawn were followed-up as routine care.

11.6. Clearly indicate person(s) responsible for payment for treatment of complications and adverse effects

None

11.7. Compensation for research participant

Yes, please provide detail:.....

No, please provide reasons: there was pragmatic trial and routine preterm care.

11.8. Does the study involve biological specimen collection? If yes, also explain how the investigator manages the leftover specimen.

None

